## 9.4.3 Secondary Endpoint(s)

#### For Parts 1 and 2:

• Establish the PK profile, including estimating the following parameters: AUC, CL and  $V_D$ ,  $C_{max}$ ,  $T_{max}$ ,  $C_{trough}$ , and  $T_{1/2}$ 

#### For Part 2:

- Evaluate anti-tumor activity according to RECIST 1.1 (Eisenhauer et al, 2009), including the following:
  - ORR defined as the proportion of patients in whom a CR or PR is observed as best overall response.
  - o DCR defined as the proportion of patients in whom a CR or PR or SD (assessed at least 6 weeks after first dose) is observed as best overall response.
  - DOR defined as the time from first objective response (CR or PR) to the first occurrence of objective tumor progression (PD) or death from any cause, whichever occurs first.

The ORR and DCR will be summarized with absolute and relative frequencies along with two-sided 95% Clopper-Pearson confidence intervals by cohort. Patients not meeting the criteria for CR or PR for ORR (CR or PR or SD for DCR), including those without any post-baseline tumor assessments, will be considered as non-responders.

DOR will be analyzed using Kaplan-Meier methodology as described in Section 9.4.1.

## 9.4.4 Exploratory Endpoint(s)

#### For Part 2:

Exploratory endpoints include evaluation of anti-tumor activity according to iRECIST:

- iORR defined as the proportion of patients in whom a iCR or iPR is observed as best overall response.
- iDCR defined as the proportion of patients in whom a iCR or iPR or iSD (assessed at least 6 weeks after first dose) is observed as best overall response.
- iDOR defined as the time from first objective response (iCR or iPR) to the first occurrence of objective tumor progression (iCPD) or death from any cause, whichever occurs first.

The iORR and iDCR will be summarized with absolute and relative frequencies along with two-sided 95% Clopper-Pearson confidence intervals by cohort. Patients not meeting the criteria for iCR or iPR for iORR (iCR or iPR or iSD for iDCR), including those without any post-baseline tumor assessments, will be considered as non-responders.

iDOR will be analyzed using Kaplan-Meier methodology as described in Section 9.4.1.

If too few responders are observed, this exploratory analysis may be omitted.

A preliminary assessment of efficacy will also be included based on evaluation of:

- PFS defined as the time from first dose of BNT411 to first occurrence of objective tumor progression, or death from any cause, whichever occurs first.
- OS defined as the time from first dose of BNT411 to death from any cause.

PFS and OS will be analyzed using Kaplan-Meier methodology as described in Section 9.4.1.

#### For Parts 1 and 2:

A preliminary assessment of biomarkers that might act as pharmacodynamics, anti-tumor, and safety indicators will also be included:

• assess the pharmacodynamics based on immune system activation as shown by changes in select cytokines and other activation markers.

#### 9.4.5 Other Safety Analyses

Other safety analyses will be detailed in the statistical analysis plan (SAP).

#### 9.4.6 Other Analyses

Other analyses will be detailed in the SAP.

# 9.5 Interim Analyses

No formal interim analysis is planned. However, data will be reviewed by the SRC after each cohort. The main statistical analysis will be performed once all patients have completed treatment and safety follow-up.

# 9.6 Safety Review Committee (SRC)

A Safety Review Committee (SRC), composed of the investigators and the sponsor's representatives will assess the cumulative safety data (e.g. SAEs, AEs, laboratory data and DLTs where applicable) collected during the trial to help ensure patient's safety.

The SRC will make recommendations for the RP2D at the end of both Parts 1A and 1B and will recommend whether to activate the expansion phase (Part 2).

Meetings with the SRC will take place at the time points outlined in the latest version of the signed SRC charter.

If a toxic dose is reached, the Medical Monitor will email the investigators and site staff to inform them that recruitment has been suspended pending review by the SRC. If the email is not acknowledged, the site will be telephoned until contact with the appropriate site staff is made. Investigators and site staff who do not attend SRC meetings will be provided with an email update of all SRC decisions within 24 hours of each meeting.

# 10 Supporting Documentation and Operational Considerations

# 10.1 Appendix 1: Regulatory, Ethical, and Trial Oversight Considerations

#### 10.1.1 Regulatory and Ethical Considerations

- This trial will be conducted in accordance with the protocol and with the following:
  - Consensus ethical principles derived from international guidelines including the Declaration of Helsinki and Council for International Organizations of Medical Sciences (CIOMS) International Ethical Guidelines
  - o Applicable ICH Good Clinical Practice (GCP) Guidelines
  - o Applicable laws and regulations
- The protocol, protocol amendments, ICF, Investigator Brochure, and other relevant documents (e.g. advertisements) must be submitted to an IRB/IEC by the investigator and reviewed and approved by the IRB/IEC before the trial is initiated.
- Any amendments to the protocol will require IRB/IEC approval before implementation
  of changes made to the trial design, except for changes necessary to eliminate an
  immediate hazard to trial patients.
- The investigator will be responsible for the following:
  - Providing written summaries of the status of the trial to the IRB/IEC annually or more frequently in accordance with the requirements, policies, and procedures established by the IRB/IEC
  - Notifying the IRB/IEC of SAEs or other significant safety findings as required by IRB/IEC procedures
  - o Providing oversight of the conduct of the trial at the site and adherence to requirements of 21 CFR, ICH guidelines, the IRB/IEC, European regulation 536/2014 for clinical studies (if applicable), and all other applicable local regulations

#### 10.1.2 Financial Disclosure

Investigators and sub-investigators will provide the sponsor with sufficient, accurate financial information as requested to allow the sponsor to submit complete and accurate financial certification or disclosure statements to the appropriate regulatory authorities. Investigators are responsible for providing information on financial interests during the course of the trial and for 1 year after completion of the trial.

#### 10.1.3 Informed Consent Process

- The investigator or his/her representative will explain the nature of the trial to the patient or his/her legally authorized representative and answer all questions regarding the trial.
- Patients must be informed that their participation is voluntary. Patients or their legally authorized representative will be required to sign a statement of informed consent that meets the requirements of 21 CFR 50, local regulations, ICH guidelines, Health

Insurance Portability and Accountability Act (HIPAA) requirements, where applicable, and the IRB/IEC or trial center.

- The medical record must include a statement that written informed consent was obtained before the patient was enrolled in the trial and the date the written consent was obtained. The authorized person obtaining the informed consent must also sign the ICF.
- Patients must be re-consented to the most current version of the ICF(s) during their participation in the trial.
- A copy of the ICF(s) must be provided to the patient or the patient's legally authorized representative.
- Patients who are rescreened are required to sign a new ICF.

The ICF will contain a separate section that addresses the use of remaining mandatory samples for optional exploratory research. The investigator or authorized designee will explain to each patient the objectives of the exploratory research. Patients will be told that they are free to refuse to participate and may withdraw their consent at any time and for any reason during the storage period. A separate signature will be required to document a patient's agreement to allow any remaining specimens to be used for exploratory research. Patients who decline to participate in this optional research will not provide this separate signature.

#### 10.1.4 Data Protection

- Patients will be assigned a unique identifier by the sponsor. Any patient records or datasets that are transferred to the sponsor will contain the identifier only; patient names or any information which would make the patient identifiable will not be transferred.
- The patient must be informed that his/her personal trial-related data will be used by the sponsor in accordance with local data protection law. The level of disclosure must also be explained to the patient who will be required to give consent for their data to be used as described in the informed consent
- The patient must be informed that his/her medical records may be examined by Clinical Quality Assurance auditors or other authorized personnel appointed by the sponsor, by appropriate IRB/IEC members, and by inspectors from regulatory authorities.

#### **10.1.5 Data Quality Assurance**

- All patient data relating to the trial will be recorded on electronic CRF (eCRF) unless transmitted to the sponsor or designee electronically (e.g. laboratory data). The investigator is responsible for verifying that data entries are accurate and correct by electronically signing the eCRF.
- The investigator must maintain accurate documentation (source data) that supports the information entered in the eCRF.
- The investigator must permit trial-related monitoring, audits, IRB/IEC review, and regulatory agency inspections and provide direct access to source data documents.

- Monitoring details describing strategy (e.g. risk-based initiatives in operations and quality such as Risk Management and Mitigation Strategies and Analytical Risk-Based Monitoring), methods, responsibilities and requirements, including handling of noncompliance issues and monitoring techniques (central, remote, or on-site monitoring) are provided in the Monitoring Plan.
- The sponsor or designee is responsible for the data management of this trial including quality checking of the data.
- The sponsor assumes accountability for actions delegated to other patients (e.g. Contract Research Organizations).
- Trial monitors will perform ongoing source data verification to confirm that data
  entered into the eCRF by authorized site personnel are accurate, complete, and
  verifiable from source documents; that the safety and rights of patients are being
  protected; and that the trial is being conducted in accordance with the currently
  approved protocol and any other trial agreements, ICH GCP, and all applicable
  regulatory requirements.
- Records and documents, including signed ICFs, pertaining to the conduct of this trial
  must be retained by the investigator for 25 years after trial completion unless local
  regulations or institutional policies require a longer retention period. No records may be
  destroyed during the retention period without the written approval of the sponsor. No
  records may be transferred to another location or party without written notification to
  the sponsor.

#### 10.1.6 Source Documents

- Source documents provide evidence for the existence of the patient and substantiate the integrity of the data collected. Source documents are filed at the investigator's site.
- Data entered in the eCRF that are transcribed from source documents must be consistent
  with the source documents or the discrepancies must be explained. The investigator
  may need to request previous medical records or transfer records, depending on the
  trial. Also, current medical records must be available.
- Definition of what constitutes source data can be found in the ICH Guideline for Good Clinical Practice.

#### 10.1.7 Trial and Site Start and Closure

The trial start date is the date on which the clinical trial will be open for recruitment of patients.

The first act of recruitment is the signing of the ICF by the first patient and will be the trial start date.

The sponsor designee reserves the right to close the trial site or terminate the trial at any time for any reason at the sole discretion of the sponsor. Trial sites will be closed upon trial completion. A trial site is considered closed when all required documents and trial supplies have been collected and a trial-site closure visit has been performed.

The investigator may initiate trial-site closure at any time, provided there is reasonable cause and sufficient notice is given in advance of the intended termination.

Reasons for the early closure of a trial site by the sponsor or investigator may include but are not limited to:

- Failure of the investigator to comply with the protocol, the requirements of the IRB/IEC or local health authorities, the sponsor's procedures, or GCP guidelines
- Inadequate recruitment of patients by the investigator
- Discontinuation of further trial treatment development

If the trial is prematurely terminated or suspended, the sponsor shall promptly inform the investigators, the IECs/IRBs, the regulatory authorities, and any contract research organization(s) used in the trial of the reason for termination or suspension, as specified by the applicable regulatory requirements. The investigator shall promptly inform the patient and should assure appropriate patient therapy and/or follow-up.

## **10.1.8 Publication Policy**

- The results of this trial may be published or presented at scientific meetings. If this is foreseen, the investigator agrees to submit all manuscripts or abstracts to the sponsor before submission. This allows the sponsor to protect proprietary information and to provide comments.
- The sponsor will comply with the requirements for publication of trial results. In accordance with standard editorial and ethical practice, the sponsor will generally support publication of multicenter studies only in their entirety and not as individual site data. In this case, a coordinating investigator will be designated by mutual agreement.
- Authorship will be determined by mutual agreement and in line with International Committee of Medical Journal Editors authorship requirements.
- The overall publication policy for the trial data is addressed in the clinical agreement for each investigator site.

#### 10.1.9 Dissemination of Clinical Trial Data

A final ICH E3 conform report integrating all trial results will be prepared by the sponsor. In all cases, trial results will be reported in an objective, accurate, balanced, and complete manner and are reported regardless of the outcome of the trial or the country in which the trial was conducted.

Clinical trial data and documentation will be disseminated as required per applicable laws and regulations, e.g., the European Union (EU) Regulation No 536/2014, EU Regulation 1049/2001, and the US Final Rule, which implements Section 801 of the Food and Drug Administration Amendments Act (FDAAA 801). Clinical documents under such laws includes protocols and protocol amendments, SAPs, ICH E3 clinical study reports.

This trial will be registered, and trial results be publicly posted, on publicly accessible trial registries (e.g., ClinicalTrials.gov, EU Clinical Trials Register, etc.) as required per applicable laws and regulations.

If this clinical trial is used to support marketing authorization packages/submissions, the sponsor will comply with the EU Policy 0070, the proactive publication of clinical data on the EMA website. Clinical data, under Phase 1 of this policy, includes clinical overviews, clinical summaries, ICH E3 clinical study reports, and appendices containing the protocol and protocol amendments, sample CRFs, and statistical methods. under Phase 2 of this policy, "clinical data" includes the publishing of individual patient data.

Even if not required by applicable laws and regulations, this trial will be registered, and trial results be publicly posted on ClinicalTrials.gov.

The results for all primary and secondary outcome measures, irrespective of outcome, will be submitted for publication in academic journals (for further details, see Section 10.1.8).

# **10.2** Appendix 2: Clinical Laboratory Tests

The tests detailed in Table 10-1 will be performed by either local or central laboratories as detailed in the relevant footnotes to Table 1-1 and Table 1-2.

- If a sample is required for local and central assessment/ analysis, it is important that the sample for central analysis is obtained at the same time as the local sample. Additionally, if the local laboratory results are used to make either a trial treatment decision or response evaluation, the results must be entered into the eCRF.
- Protocol-specific requirements for inclusion of patients, including pregnancy testing, are detailed in Section 5.1 of the protocol.
- Additional tests may be performed at any time during the trial as determined necessary by the investigator or required by local regulations.

**Table 10-1:** Protocol-Required Safety Laboratory Assessments

Laboratory Assessments	Parameters					
Hematology	Platelet Count	RBC Indices: Mean corpuscular vo (MCV) Mean corpuscular hemoglobin (MCH)	olume with Neut Lym Mon Eosii	White blood cell (WBC) count with Differential: Neutrophils Lymphocytes Monocytes Eosinophils Basophils		
	Red blood cell (RBC) Count					
	Hemoglobin					
Biochemistry	Hematocrit Blood urea nitrogen (BUN)	Potassium, Magnesium Chloride, Phosphate (inorg.) Lactate dehydrogenase (LDH), Amylase	Aspartate Aminotransfo (AST)/ Serur Glutamic- Oxaloacetic Transaminas (SGOT)	e e		
	Creatinine	Sodium	Alanine Aminotransfo (ALT)/ Serui Glutamic-Py Transaminas (SGPT)	m ruvic e		
	Glucose (non-fasting)	Calcium	Alkaline phosphatase	Albumin		
Routine Urinalysis  Coagulation Factors	
 
Specific gravity
 
pH, glucose, protein, blood, ketones, bilirubin, urobilirubinogen, nitrite and leukocyte esterase
 
Microscopic examination (if blood or protein is abnormal)
 
Prothrombin time
 
Activated partial thromboplastin time (aPTT)
 
International normalized ratio (INR)
 
					
Endocrine Tests	TSH, free T3 and free T4					
Pharmacodynamics and biomarkers	Blood sampling for cytokine analysis, immune phenotyping					
Serology	• Country specific procedure for Germany: To confirm trial eligibility, an active infection with HIV/Hepatitis B or C should be ruled out by serum blood test of hepatitis B surface antigen (HBsAg), antibody to hepatitis B core antigen (anti-HBc), antibody to hepatitis B surface antigen (anti-HBs), antibody against hepatitis C virus (anti-HCV), antibody against HIV-1 and -2 (anti-HIV 1/2).					
Other Screening Tests	Highly sensitive serum human chorionic gonadotropin (hCG) pregnancy test (as needed for women of childbearing potential)					

Investigators must document their review of each laboratory safety report. The results of each test must be entered into the eCRF.

# 10.3 Appendix 3: Adverse Events: Definitions and Procedures for Recording, Evaluating, Follow-up, and Reporting

#### 10.3.1 Definition of AE

#### **AE Definition**

- An AE is any untoward medical occurrence in a patient or clinical trial patient, temporally associated with the use of trial treatment, whether or not considered related to the trial treatment.
- NOTE: An AE can therefore be any unfavorable and unintended sign (including an abnormal laboratory finding), symptom, or disease (new or exacerbated) temporally associated with the use of trial treatment.
- A treatment-emergent AE (TEAE) is defined as any AE with an onset date on or after the first administration of trial treatment (if the AE was absent before the first administration of trial treatment) or worsened after the first administration of trial treatment (if the AE was present before the first administration of trial treatment). AEs occurring after the period of observation (60 days after last treatment dose) will be considered as treatment-emergent only if assessed as related to the trial treatment by the investigator.

## **Events Meeting the AE Definition**

- New conditions or worsening of pre-existing conditions detected or diagnosed after signing patient informed consent
- Any abnormal laboratory test results (hematology, biochemistry, endocrine parameters, coagulation profile or urinalysis) or other safety assessments (e.g. ECGs, radiological scans, vital signs measurements), including those that worsen from baseline, considered **clinically significant** in the medical and scientific judgment of the investigator (i.e. medical conditions that have medical consequences for the subject) or laboratory value or other clinical test that is associated with symptoms or leads to a change in trial treatment or concomitant treatment or discontinuation from trial treatment.
- Any exacerbation of pre-existing medical condition (a worsening in the character, frequency, or severity of a known medical condition). This includes any condition resulting from concomitant illnesses, reactions to concomitant medications, or progression of concomitant disease states.
- Recurrence of a previous medical condition not present at baseline or exacerbation of a chronic or intermittent pre-existing condition including either an increase in frequency and/or intensity of the condition.
- Signs, symptoms, or the clinical sequelae of a suspected drug-drug interaction.

## **Events Meeting the AE Definition**

- Signs, symptoms, or the clinical sequelae of a suspected overdose of either trial treatment or a concomitant medication. Overdose per se will not be reported as an AE/SAE unless it is an intentional overdose taken with possible suicidal/self-harming intent. Such overdoses should be reported regardless of sequelae.
- Trial procedure related AEs (caused by a protocol-mandated intervention, including those that occur prior to assignment of trial treatment, such as tumor biopsies).
- Lack of efficacy" or "failure of expected pharmacological action" per se will not be reported as an AE or SAE. Such instances will be captured in the efficacy assessments. However, the signs, symptoms, and/or clinical sequelae resulting from lack of efficacy will be reported as an AE or SAE if they fulfil the definition of an AE or SAE.

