# 8.7.7 Disease-Related Events and/or Disease-Related Outcomes Not Qualifying as AEs or SAEs

The progression of underlying disease (e.g., new metastases) during trial participation is not considered as an AE.

Because disease progression is common for patients with cancer, it will not be reported according to the standard process for expedited reporting of an SAE even though the event may meet the definition of a SAE. These events will be recorded on the corresponding page in the patient's eCRF.

NOTE: symptoms resulting from the progression and clearly stated as related to the progressive disease (PD) and fatal cases clearly related to the progression will not be documented and reported as AEs and SAEs. However, specific symptoms at time of progression that are considered to be caused by other reason, and fatal cases where other reason rather than the PD may not be discarded, will have to be documented as AEs and reported as SAEs if applicable.

In Germany only: deaths related to disease progression will be reported as AEs or SAEs.

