#### 9 Statistics

## 9.1 Statistical Hypotheses

No statistical hypotheses are planned to be tested in this trial.

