#### 9.4.2 Primary Endpoint(s)

The primary objective of the trial is to assess the safety profile of the regimen based on the following endpoints:

- Occurrence of dose limiting toxicities (DLTs) within a patient during the DLT evaluation period
- Occurrence of treatment-emergent adverse events (TEAE) within a patient including grade ≥3, serious, fatal TEAE by relationship
- Occurrence of dose reduction and discontinuation of BNT411 within a patient due to treatment-emergent adverse events (TEAE)

And to determine the MTD and/or RP2D defined as follows:

- MTD the highest tolerated dose
- RP2D based on integrated evaluation of safety, tolerability, clinical benefit, PK, and pharmacodynamics data, for all dose levels tested.

A treatment emergent AE is defined as any AE with an onset date on or after the first administration of trial treatment (if the AE was absent before the first administration of trial treatment) or worsened after the first administration of trial treatment (if the AE was present before the first administration of trial treatment). AEs with an onset date more than 60 days after the last administration of trial treatment will be considered as treatment emergent only if assessed as related to trial treatment by the investigator. Treatment-emergent AEs will be summarized overall and by treatment arm. The trial treatment includes BNT411, atezolizumab, carboplatin, and etoposide.

AEs will be coded using the most recent version of Medical Dictionary for Regulatory Activities (MedDRA®) coding system to get a System Organ Class (SOC) and Preferred Term (PT) for each AE and graded for severity using NCI CTCAE v5.0.

The number and percentage of patients reporting at least one AE will be summarized by PT nested within SOC for each of the following AE types:

- any AE
- related AE
- Grade >3 AE
- related Grade ≥3 AE
- any SAE
- related SAE
- SAE leading to death
- AE leading to dose reduction
- AE leading to permanent discontinuation of treatment
- DLT.

Moreover, the number and percentage of patients with any AE will be summarized by worst NCI CTCAE grade by PT nested within SOC.

DLTs will be presented in terms of listings presenting the reported term and MedDRA PT and SOC term, its time of onset, duration, and outcome, relationship, NCI CTCAE grade, and seriousness including dose exposure data.

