## **Events NOT Meeting the AE Definition**

- Any clinically significant abnormal laboratory findings or other abnormal safety assessments which are associated with the underlying disease, unless judged by the investigator to be more severe than anticipated for the patient's condition. The disease/disorder being studied or expected progression, signs, or symptoms of the disease/disorder being studied, unless more severe than expected for the patient's condition. However, specific symptoms at time of progression that are considered to be caused by other reason, and fatal cases where other reason rather than the PD may not be discarded and will have to be documented as AEs and reported as SAEs if applicable. In Germany only: Deaths related to disease progression will be documented as AEs and reported as SAEs.
- Any abnormal laboratory findings which are evaluated and documented in the source data as not clinically significant (e.g., an abnormal laboratory value without any clinical manifestation, such as transient lymphopenia after infusion of BNT411 due to redistribution), should not be documented as an AE.
- The disease/disorder being studied, or anticipated progression, signs, or symptoms of the disease/disorder being studied, unless more severe than anticipated for the patient's condition
- Medical or surgical procedure (e.g., endoscopy, appendectomy): the condition that leads to the procedure is the AE.
- Situations in which an untoward medical occurrence did not occur (social and/or convenience admission to a hospital).
- Anticipated day-to-day fluctuations of pre-existing disease(s) or condition(s) present or detected at the start of the trial that do not worsen.

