8.5.2 Adverse events

This section includes the description of the analysis planned for the primary endpoints on this trial.

AEs will be coded using the most recent version of Medical Dictionary for Regulatory Activities (MedDRA®) coding system version 26.0 or higher to get a SOC and PT for each AE and graded for severity using NCI CTCAE v5.0. In case a patient has an AE with missing relationship status, the event will be assumed to be related and associated with the treatment received in the summaries (will be listed as collected in the listings). No imputation for missing NCI-CTC grades will be performed.

A treatment-emergent AE (TEAE) is defined as any AE with an onset date on or after the first administration of trial treatment (BNT411 in part1A and BNT411, atezolizumab, carboplatin, and etoposide in Part 1B) (if the AE was absent before the first administration of trial treatment) or worsened after the first administration of trial treatment (if the AE was present before the first administration of trial treatment). AEs with an onset date more than 60 days after the last administration of trial treatment will be considered as treatment-emergent only if assessed as related to trial treatment (BNT411 for Part 1A and BNT411, atezolizumab, carboplatin, and etoposide for Part 1B) by the investigator.

Treatment-emergent AEs will be summarized by cohort and trial part and total within trial part. In addition, treatment-related TEAEs will be summarized by cohort and trial treatment (BNT411, atezolizumab, carboplatin, and etoposide) within trial part.

Only TEAE data will be summarized for the Safety set for each trial part (Part 1A and Part 1B). Non-TEAEs will be listed only.

Dose-limiting toxicities

In general, a DLT for a drug or other treatment is defined as one or more AEs that prevents an increase of the dose level of that treatment (for details on dose escalation decision rules see Appendix 5).

Serious AEs (SAEs), non-serious grade ≥ 3 AEs and clinically significant abnormal laboratory values grade ≥ 3 will be collected and assessed for DLTs (for each dose level during the first cycle). Common Terminology Criteria for Adverse Events (NCI CTCAE) v.5.0 will be used to grade the intensity of AEs.

More details regarding DLTs can be found in the Section 6.6 of the CTP.

For the additional rules and considerations of MTD and RP2D other than what was already defined in Section 1.1, see Section 4.1.1.2 of the CTP.

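### Protocol 8.7.7 and 10.3.1 give opposite recording rules for a non-fatal symptom clearly due to progression and worse than expected, so all-causality Grade ≥3 and serious TEAE counts can depend on which section a site follows

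*Protocol*

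**What the plan says.** Protocol 10.3.1 starts from a broad definition: "An AE is any untoward medical occurrence in a patient or clinical trial patient, temporally associated with the use of trial treatment". Relatedness plays no part in it.

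The list of events not meeting that definition (also 10.3.1) takes out the disease under study and its "expected progression, signs, or symptoms of the disease/disorder being studied, unless more severe than expected" for that patient. A later bullet in the same list repeats the exclusion and its exception, with anticipated in place of expected.

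Protocol 8.7.7 deals with the same subject in a NOTE. It covers "symptoms resulting from the progression and clearly stated as related to the progressive disease (PD") and says that these are not to be documented or reported as AEs or SAEs. The NOTE has no severity exception. Its only way back into AE recording is for symptoms at progression that are thought to have some other cause.

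The list of events that do meet the definition (10.3.1) adds that "the signs, symptoms, and/or clinical sequelae resulting from lack of efficacy will be reported as an AE or SAE if they fulfil the definition" for either category.

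The affected endpoint is primary. Protocol 9.4.2 counts TEAEs "within a patient including grade ≥3, serious, fatal TEAE by relationship". SAP 8.5.2 states: "Only TEAE data will be summarized for the Safety set for each trial part".

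**The concern.** A site cannot follow both sections for a progression symptom that is worse than expected. Under 10.3.1 it is an AE, and an SAE if a seriousness criterion is met; under 8.7.7 it is not recorded as either. An event left out under 8.7.7 reaches no AE table or listing, and the SAP has no rule that would identify or restore it.

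The events in dispute are by definition the worse ones, so they are likely to fall in the Grade ≥3 and serious rows. Part 1A takes patients for whom no standard therapy is likely to help, or who are not candidates for it (inclusion criterion 1). The TEAE window runs to 60 days after the last dose of trial treatment, so progression inside the window is plausible. Cohorts are small, so one patient recorded differently can create or hide an apparent difference between dose levels with no change in what the drug does.

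**Working it through.** There is no stated figure to reproduce. Protocol 9.1 says "No statistical hypotheses are planned to be tested in this trial", and the sample size follows the 3+3 design. The check is a comparison of the rules, followed by simple arithmetic for scale.

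**Step 1. Apply each section to the same non-fatal symptom.**

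| Symptom | Protocol 10.3.1 | Protocol 8.7.7 |
|---|---|---|
| Clearly due to progression, within expectation for the patient | Not an AE | Not an AE |
| Clearly due to progression, worse than expected for the patient | AE; SAE if serious | Not an AE or SAE |
| Present at progression, attributed to another cause | AE | AE |

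The sections agree in the first and third rows and conflict in the second.

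**Step 2. Place the lack-of-efficacy bullet.** It applies only if the AE or SAE definition is met, and the adjoining list in the same section says which progression symptoms fall outside that definition. Read together, they give the 10.3.1 column above. A site that reads the bullet against the broad opening definition alone could record every progression symptom, so the bullet is ambiguous, but it is not a separate rule.

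**Step 3. Look for text that settles the conflict.** The progression exemption in 10.3.3 covers deaths only. The Germany-only clauses on progression also concern deaths. Protocol 8.7 refers the reader to Section 10.3 for the AE and SAE definitions, which favours 10.3.1 but does not cancel the explicit instruction in 8.7.7. SAP 8.5.2 is silent.

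**Step 4. Size of one reclassified patient.** AE percentages use the number of patients in the analysis set (SAP 8.1), and each patient counts once per row. If a patient has no other event in that row, recording or not recording the symptom moves the cohort rate by 100/n points. Illustrative n: 3 and 6 (Protocol 9.2, evaluable patients per cohort) and 14 (Protocol 4.1.1.1, backfill maximum).

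- n=3: 100/3 = 33.3 points
- n=6: 100/6 = 16.7 points
- n=14: 100/14 = 7.1 points

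**Step 5. Chance that a cohort contains at least one such patient.** This is 1 − (1 − q)^n, where q is the proportion of patients with a symptom of the second-row kind. The documents give no value for q, so 5%, 10% and 20% are assumptions used only to show the range.

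| n | q = 5% | q = 10% | q = 20% |
|---|---|---|---|
| 3 | 14.3% | 27.1% | 48.8% |
| 6 | 26.5% | 46.9% | 73.8% |
| 14 | 51.2% | 77.1% | 95.6% |

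For example, at n=6 and q=10%: 1 − 0.9^6 = 1 − 0.531 = 46.9%. These are chances that a disputed patient exists, not that sites actually differ in how they record that patient.

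**The case against.** The strongest reply is that the overlap is narrow. Section 8.7.7 reaches only symptoms clearly stated to be due to progression, and a symptom out of proportion to the patient's disease is less likely to be so described. Both sections record symptoms with another cause, and 8.7 already points to 10.3 for definitions. This stands as a limit on size. It does not remove the conflict, because a symptom can be clearly tumour-related and still worse than expected.

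The second reply is that little depends on it. No hypothesis is tested, and SAP 8.1 rules out formal comparisons between cohorts. DLTs exclude toxicities clearly related to progression (Protocol 6.6). Beyond DLTs, the RP2D considerations in Protocol 4.1.1.2 look specifically at BNT411-related AEs, and the SAP tabulates related Grade ≥3 and related serious TEAEs separately. This also stands: the exposure is confined to the all-causality descriptive rows. Those rows are nevertheless part of a primary endpoint and will be read across dose levels.

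Three stronger readings are tempting, and the documents do not support them:

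- A reader might infer three competing rules, with the lack-of-efficacy bullet making all progression symptoms AEs. That drops the bullet's own condition.
- A reader might infer that every Grade 3 progression symptom is in dispute. The exception in 10.3.1 turns on expectation for the patient, not on CTCAE grade; Grade 3 tumour pain that was expected is outside AE recording under both sections.
- A reader might take an assumed rate of all severe progression symptoms, such as 15–30%, and conclude that 1–2 of 6 patients move (0.15 × 6 = 0.9; 0.30 × 6 = 1.8). That uses too wide a base, assumes that every such patient is reclassified, and ignores patients who already have another Grade ≥3 TEAE.

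**Conclusion.** The point holds as a two-way contradiction between Protocol 8.7.7 and 10.3.1, limited to non-fatal symptoms that are both clearly attributed to progression and worse than expected for the patient. Through it, the all-causality Grade ≥3 and serious TEAE counts can depend on the section a site applies. The size per patient is 33, 17 or 7 percentage points at n=3, 6 or 14, provided that the patient has no other event in the row. The overall effect cannot be estimated from the documents, because they give neither the frequency of such symptoms nor the rule that sites follow. DLT counts, and so dose escalation, are largely protected, as are the BNT411-related rows. It is a recording inconsistency worth correcting, not a flaw in the dose-finding design.

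**What to change.** Use one rule. Since Protocol 8.7 sends the reader to Section 10.3 for the AE and SAE definitions, add to the NOTE in 8.7.7 the same severity exception that 10.3.1 carries: a progression symptom worse than expected for that patient is recorded as an AE, and as an SAE if serious. Then cross-refer the lack-of-efficacy bullet in 10.3.1 to that rule so that it cannot be read alone.

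For data already collected, state in the clinical trial report that the all-causality Grade ≥3 and serious TEAE rows may include or omit progression symptoms depending on the section a site applied, and read cohort differences in those rows beside the related-TEAE rows.

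A repeat of those rows without progression-attributed events is optional. Protocol 10.3.3 lets causality be recorded simply as related or not related, and no AE field for attribution to progression is described, so the repeat would need medical review of recorded terms. It also could not recover events that were never recorded.

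The cost is a wording change in two protocol sections, a short statement in the report and slightly more AE recording at sites.
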